7.2 Duplicate Data

For unplanned duplicate data within a protocol-specified visit, the last measured value will be used for the analysis. If it is not possible to identify the “last measured value” the average of the duplicate values will be used. No data will be excluded. All collected data will be listed.

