6.1.2 Efficacy / Psychometric Assessments

All raters for the efficacy assessments need to be trained and qualified on the administration of the scales. A qualified rater is required for the administration of the SIB, NPI and MMSE-2.

The same qualified rater should perform a given Efficacy/Psychometric Assessment at approximately the same time of day for a given subject throughout the study. All changes in raters for a given assessments must be noted in the subject’s source documents. The caregiver designated to provide assessments (ADCS-ADL-Sev and NPI) at the start of the study should be the same individual throughout the study. Should a change be necessary during the course of the study, the reason for the change and the first corresponding visit must be noted in the subject’s source document.

All psychometric tests performed on study subjects on the same day should be administered in the following order: SIB followed by MMSE-2, except at the screening visit as described in Section 6.2.1. If the MMSE-2 score obtained at screening does not fall within the 4-15 range for inclusion, no further screening tests should be performed. Efficacy tests at subsequent visits should be administered prior to dosing.

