8.3.2 Clinical Laboratory Evaluations

All available results of the clinical laboratory evaluations will be listed and summarized as follows:

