8.3.2.2 Individual Subject Changes (Shift Tables)

Individual subject changes will be identified through shift tables. Shift tables will be presented for each laboratory parameter with counts and percentages of subjects, by treatment group and time point, for shift (change) from baseline, using the normal ranges from the laboratory.

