8.3.2.3 Individual Clinically Significant Abnormalities

Clinically significant laboratory abnormalities (i.e., those laboratory abnormalities recorded as AEs) will be listed.

All results of laboratory evaluations will be presented as by-subject listings.

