8.3.5 ECG

All ECG findings will be listed and/or summarized. Shift tables will also be presented to show any abnormality shifts from baseline to post baseline visits.

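### The last-value rule for duplicates in SAP 7.2, with no worst-value table, lets a normal same-visit repeat replace an abnormal lab, ECG or examination result in the safety tables

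*SAP*

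**What the plan says.** SAP 7.2 governs repeated measurements: "For unplanned duplicate data within a protocol-specified visit, the last measured value will be used for the analysis". If the last value cannot be identified, the duplicates are averaged. The section adds "No data will be excluded. All collected data will be listed". It draws no line between safety and efficacy, between pre-dose and post-dose, or between a recheck of an abnormal result and a clerical duplicate.

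For laboratory data, SAP 8.3.2 opens with "All available results of the clinical laboratory evaluations will be listed and summarized as follows". SAP 8.3.2.2 then says "Individual subject changes will be identified through shift tables"; these tables are by treatment group and time point, "for shift (change) from baseline, using the normal ranges from the laboratory". SAP 8.3.2.3 adds that "Clinically significant laboratory abnormalities (i.e., those laboratory abnormalities recorded as AEs) will be listed". For ECG (SAP 8.3.5), "Shift tables will also be presented to show any abnormality shifts from baseline to post baseline visits"; SAP 8.3.3 has the same provision for physical examination. SAP 8.3.4 gives vital signs descriptive tabulations by time point and no shift table. No section plans a worst-post-baseline or any-time abnormality table.

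For efficacy, Protocol 6.1.2 states "Efficacy tests at subsequent visits should be administered prior to dosing". The schedule of activities marks SIB and MMSE-2 as pre-dose at Weeks 5 and 9.

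**The concern.** A repeat prompted by an abnormal result is selected on that result, so regression to the mean makes the repeat more likely to be normal even if the patient has not changed. A last-value rule then keeps the second number and drops the one that raised the question. Safety and tolerability are part of the primary objective, and Protocol 9.3 plans no formal safety tests. The descriptive tables, with the adverse event tables, therefore carry the comparison between arms. If they under-count transient abnormalities, a modest signal is harder to see.

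On efficacy, the SAP rule turns on the order of measurement, whereas the protocol rule turns on timing relative to the infusion. Where the two disagree, the SAP picks the value that the protocol did not intend.

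**Working it through.** The plan gives no figure for duplicates, so the main check is textual. An illustration of size follows.

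**1. What happens to an abnormal first value with a normal same-visit repeat**

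| Output | Value used | Is the abnormality visible? |
|---|---|---|
| Lab by-visit summary and shift table (SAP 8.3.2.1, 8.3.2.2) | last | no |
| ECG and physical-examination shift tables (SAP 8.3.5, 8.3.3) | last | no |
| Vital-sign tabulations (SAP 8.3.4) | last | no (no shift table exists) |
| Listings (SAP 7.2) | all | yes |
| TEAE tables (SAP 8.3.1) | adverse events | only if recorded as an AE |

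The opening of SAP 8.3.2 promises that all available lab results are summarized as well as listed. The subsections that follow do not say how two values at one time point enter a table, so SAP 7.2 is the only operative rule and the two statements need reconciling.

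**2. Illustration of size (assumptions, not document figures)**

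Let the first and repeat values Z1 and Z2 be standard bivariate normal with correlation r, for a subject whose state does not change. Let the upper limit be c = 1.96, so that p = P(Z1 > c) = 0.025. The share of first-abnormal values that are normal on repeat is

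s = 1 − P(Z1 > c and Z2 > c) / P(Z1 > c).

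- r = 0.8: joint probability 0.0110, s = 1 − 0.0110/0.025 = 0.56.
- r = 0.9: joint probability 0.0148, s = 1 − 0.0148/0.025 = 0.41.

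Over a wider range (2.5% to 10% abnormal, r from 0.5 to 0.9), s runs from about 31% to 82%.

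Only values that are actually repeated at that visit can be replaced. If a fraction f of abnormal first values is repeated, the tabulated rate is p(1 − f·s). With p = 2.5%:

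- f = 1: 2.5 × (1 − 0.56) = 1.1%, or 2.5 × (1 − 0.41) = 1.5%.
- f = 0.5: 2.5 × (1 − 0.28) = 1.8%, or 2.5 × (1 − 0.205) = 2.0%.
- f = 0: no effect.

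The documents do not give f.

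**3. Effect on an arm difference**

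In the same model, take f = 1 and shift one arm up by one SD. First-value rates are 16.9% and 2.5%, a difference of 14.4 points and a ratio of about 6.7. Last-value rates are 10.5% and 1.1% (r = 0.8), or 12.4% and 1.5% (r = 0.9), giving differences of 9.4 and 10.9 points. The absolute difference shrinks by about a quarter to a third. The ratio does not shrink; it rises to between 8 and 10.

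**4. The efficacy side**

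SIB is given after baseline at Weeks 5, 9, 13 and 15, and only Weeks 5 and 9 have an infusion (Protocol Table 1). SAP 7.1 limits baseline to values before treatment. A same-visit post-infusion repeat can therefore displace the scheduled test only at Weeks 5 and 9. These visits feed the secondary SIB changes, the slope and the exploratory MMSE-2. They may also feed the imputation, since SAP 7.3.1 does not list the imputation variables beyond the stratification factor. Protocol 5.7 allows a short-acting sedative for the infusion once efficacy testing is done, so a test repeated afterwards would not necessarily be taken under the same conditions.

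**The case against.** The strongest reply is that the rule rarely bites. It covers only duplicates within a scheduled visit. Lab samples go to a central laboratory (Protocol 6.1.1.1), so an abnormal result is not normally known before the subject leaves, and a redraw would usually need a return trip. The SAP gives no analysis windows and does not say whether such a redraw belongs to the visit. Immediate repeats are most plausible for vital signs, which have no shift table. This stands: it limits how often replacement occurs and is why no frequency can be given.

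Second, abnormalities that matter clinically have another route into the tables. A clinically significant abnormal lab finding falls within the adverse event definition (Protocol 7.0), and TEAEs are tabulated by arm. This also stands. What drops out of the tables is the transient out-of-range value that nobody recorded as an AE.

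Third, first, last and average are all ordinary duplicate conventions, and this one is pre-specified and applied alike in both blinded arms. That is fair for by-visit summaries. It does not answer the absence of any table that captures the worst value, which is the actual gap.

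Fourth, a post-infusion SIB or MMSE-2 repeat would itself depart from the protocol, and nothing in the schedule provides for one. This stands, and it makes the efficacy part the lesser one.

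**Conclusion.** The point holds on the text of SAP 7.2 and of the table specifications. A normal same-visit repeat removes a lab, ECG or examination abnormality from the by-visit and shift tables, and no worst-value table recovers it. The direction is mainly towards under-tabulation. The size is unknown: the 41% to 56% figure rests on an assumed correlation of 0.9 to 0.8, a limit at the 97.5th percentile, and every abnormal value being repeated at its visit.

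A reader might infer three stronger things that the documents do not support:

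- That the rule conceals a real safety difference. Both blinded arms follow the same rule. Under the assumptions above, a real difference is attenuated in absolute terms, not removed.
- That abnormalities disappear from reporting. Listings keep every value, and abnormalities recorded as AEs remain in the TEAE tables.
- That the primary endpoint is at risk. Week 13 has no infusion and baseline is restricted to pre-treatment values, so neither can be displaced by a same-visit post-dose repeat.

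This is a modest weakness in safety reporting, worth correcting because the correction is cheap.

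**What to change.** 1. Add a baseline-to-worst-post-baseline shift table for labs and ECG that includes all repeats and unscheduled values and excludes samples flagged as invalid.
2. State in SAP 7.2 that, for efficacy, only assessments completed before that visit's infusion are eligible for analysis.
3. Reconcile SAP 7.2 with the opening of SAP 8.3.2, and say how repeats logged as unscheduled are treated.

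Once item 1 is in place, the by-visit convention (first or last) can stay as the sponsor prefers. The cost is SAP wording and one extra table, with no new data collection. The downside is that some spurious abnormal values will appear in the worst-value table unless they are flagged as invalid.

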7.3 Handling of Missing Data

Every effort will be made to obtain required data at each scheduled evaluation from all subjects who have been randomized to minimize missing data. However, in the event when there is missing data the following imputation methods will be used.

7.3.1 Handling of Missing Data for Efficacy Evaluations

For efficacy evaluations, multiple imputation methods will be used to handle missing data. The imputation will be carried out in SAS version 9.4 or later using PROC MI. Each imputation model will include the stratification factor (i.e., MMSE-2 score (4-9 vs. 10-15)) as a covariate in the model.

7.3.1.1 Multiple Imputation for Continuous variables

If the **missing data point is continuous in nature with monotone pattern**, predictive mean matching will be used in the model.

This method imputes a value randomly from a set of observed values whose predicted values are closest to the predicted value for the missing value from the simulated regression model.

If the **missing data point is continuous in nature with arbitrary pattern**, a fully conditional specification (FCS) will be used, using the predictive mean matching method with joint distribution for all variables.

7.3.1.2 Multiple Imputation for Categorical variables

If the **data point is categorical in nature with monotone pattern**, logistic method will be used in the model. With this method, a logistic regression model is fitted for a categorical variable with covariates. All the categorical endpoints in the study have binary classification variables, and for these based on the fitted regression model, a new logistic regression model is simulated from the posterior predictive distribution of the parameters and is used to impute the missing values for each variable.

If the **data point is categorical in nature with arbitrary pattern**, a fully conditional specification (FCS) will be used using logistic regression approach with joint distribution for all variables.

7.4 Multicenter Clinical Trials

This is a randomized study with multiple centers.

7.5 Multiple Comparisons and Multiplicity

There will be no need to adjust for multiple testing or multiplicity for this phase 2 trial. For all effectiveness endpoints, inference will be based on type I error rate of 0.05.

7.6 Covariates and Prognostic Factors

In the efficacy analysis, the stratification factors and baseline values such as age, sex, or disease severity may be used as covariates in the analysis of all the primary, secondary, and additional efficacy endpoints.

7.7 Stratification Factors and Subgroups

This is a randomized study and stratified so that the groups have similar distribution of MMSE-2 score (4-9 vs. 10-15). The stratification will ensure balance between each treatment group in each stratum.

7.8 Standard Calculations

7.8.1 Age

Age will be calculated as the number of completed years between the date of informed consent and the subject's birth date.

$$\text{Age (years)} = \text{integer of } [(\text{date of informed consent} - \text{date of birth}) / 365.25]$$

7.8.2 Height

For summary purposes height will be expressed in centimeters. Entries made in inches will be converted to centimeters using the formula noted below.

$$\text{Height (cm)} = \text{Height (in)} * 2.54$$

7.8.3 Weight

For summary purposes weight will be expressed in kilograms. Entries made in pounds will be converted to kilograms using the formula noted below.

$$\text{Weight (kg)} = \text{Weight (lb)} / 2.2046$$

7.8.4 Change from Baseline

For any of the effectiveness measurements change from baseline will be calculated using the formula noted below.

$$\text{Change from baseline} = \text{Post Baseline Measurement} - \text{Baseline Measurement}$$

8. STATISTICAL METHODS

All data collected during this study will be presented in subject data listings.

All statistical analyses will be performed using SAS[®] for Windows, version 9.4 or later. For continuous variables, descriptive statistics (n, mean, standard deviation, median, minimum and maximum) will be presented by treatment group. For categorical variables both frequencies and percentages will be presented by treatment group.

8.1 Disposition and Baseline Characteristics

8.1.1 Subject Disposition and Withdrawals

There will be a detailed accounting of all subjects that signed the informed consent to participate in this trial. The following will be summarized by treatment group:

- The number of subjects who signed the informed consent
- The number of subjects who are screen failures
- The number of subjects who are randomized
- The number of randomized subjects in each stratum
- The number of subjects who received at least one study treatment
- The number of subjects who completed the study
- The number of subjects who discontinued
 - Reasons for discontinuation prior to completion will also be summarized descriptively by treatment group.

In addition, there will also be a listing of all discontinued subjects, which will provide the clinical trial center, treatment group and the specific reason for discontinuation.

8.1.2 Demographics and Baseline Characteristics

Demographic (age, sex, race, ethnicity, height and body weight) and other basic baseline characteristics will be summarized and/or listed, descriptively, by treatment group.

Medical history and Rosen-modified Hachinski Scale results will be provided as by-subject listings.

8.1.3 Prior and Concomitant Medications

Prior and concomitant medications will be summarized.

All prior and concomitant medications recorded in the case report form will be coded to the drug substance level (*i.e.*, generic term) using the most recent version of WHO Drug dictionary.

Descriptive summaries, by treatment group, will be prepared using the coded terms. All prior and concomitant medications recorded in the case report form will be listed.

8.1.4 Treatment Administration and Compliance

All treatment administration and compliance data will be listed and summarized.

8.2 Analysis of Efficacy Data

The primary analysis will be conducted on FAS population. The CAS population will be used as a supportive analysis. All statistical tests for efficacy will be two-sided tests, with $\alpha=0.05$.

8.2.1 Primary Efficacy Endpoint

The primary endpoint for this study is the change from baseline to Week 13 in the SIB total score.

The change from baseline to Week 13 in the SIB total score will be summarized descriptively and compared using Analysis of Covariance (ANCOVA) adjusted for baseline SIB total score.

If the normality assumption is not met, a non-parametric method or a rank-ANCOVA analysis (i.e., an ANCOVA analysis on rank-transformed data) will be used.

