3. SAMPLE SIZE DETERMINATION AND RATIONALE, STATISTICAL POWER, AND SIGNIFICANCE LEVEL

Based on post hoc analyses of the NTRP 101-202 study for patients not treated with memantine, the SIB for the 20ug bryostatin group demonstrated a mean (SD) increase of 4.5 (6.8) points from baseline by Week 13. In contrast, patients not treated with memantine in the placebo arm showed a decrease in SIB scores at the 13-week time-point from baseline, giving a mean (SD) SIB change of -0.9 (6.7) points. This resulted in group difference in means of the 13-week SIB measure from baseline SIB changes of 5.4 points.

Guided by these post hoc results, power analyses were performed based on 50 patients per treatment arm, and assuming differences of between 4.0 to 5.5 points in the treatment arm-specific means of the primary outcome (e.g. the treatment effect). Table 3-1 below gives the estimated power to detect various treatment effects, assuming a two-sided alpha of 0.05. Based on these analyses, 50 patients per group will give an approximate 83% power to detect a treatment effect of 4.0 points, and an estimated power of 98% to see a treatment effect of 5.5 points. Power calculation was based the two-sample t-test of the group difference in the mean 13-week SIB changes from baseline SIB.

Table 3-1: Power to detect treatment effect sizes of between 4.0 to 5.5 points; 50 patients per group with an available primary efficacy endpoint.

Diff. in Deltas	Power	N1	N2	Two-sided Alpha
4	83%	50	50	0.05
4.5	91%	50	50	0.05

5	95%	50	50	0.05
5.5	98%	50	50	0.05

Power analyses were also performed to determine detectable effect sizes that assume an estimated dropout rate of 25% (e.g. 50 patients per group at a baseline, dropping to 37 patients per group by Week 13). Table 3-2 gives the estimated powers for treatment effects of between 4.5 and 5.5 points, assuming a 25% dropout rate. Note that a minimum treatment effect of 4.5 points can be statistically detected with at least 80% power, given 37 patients per group with a primary efficacy endpoint.

Table 3-2: Power to detect treatment effect sizes of between 4.5 to 5.5 points; 37 patients per group with an available primary efficacy endpoint.

Diff. in Deltas	Power	N1	N2	Two-sided Alpha
4.5	80%	37	37	0.05
5	88%	37	37	0.05
5.5	93%	37	37	0.05

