5. PRIMARY HYPOTHESIS TO BE TESTED

The primary hypothesis to be tested for this study is below:

H_0 : $\mu_{Active} = \mu_{Control}$ (i.e. mean change from baseline in SIB total score between the two groups is the same)

H_1 : $\mu_{Active} \neq \mu_{Control}$ (i.e. mean change from baseline in SIB total score between the two groups is different)

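### The primary ANCOVA omits the randomisation stratum, leaves other covariates optional with no selection rule, and has a non-normality fallback with no trigger and two alternatives

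*SAP*

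**What the plan says.** SAP 8.2 fixes the population (FAS, with CAS as support), two-sided testing and alpha 0.05. SAP 8.2.1 then names a model: the change to Week 13 is "compared using Analysis of Covariance (ANCOVA) adjusted for baseline SIB total score". No other covariate appears there.

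SAP 7.6 widens this: "the stratification factors and baseline values such as age, sex, or disease severity may be used as covariates in the analysis" of the primary, secondary and additional efficacy endpoints. It gives no rule for which covariates enter, no decision time and no definition of disease severity.

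Randomisation is stratified by MMSE-2 4-9 versus 10-15 (SAP 2.1 and 7.7). On missing data, SAP 7.3.1 states: "Each imputation model will include the stratification factor".

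SAP 8.2.1 also has a fallback: "If the normality assumption is not met, a non-parametric method or a rank-ANCOVA analysis" is to be used. Rank-ANCOVA is explained as ANCOVA on rank-transformed data. The non-parametric method is not named, and there is no normality test, threshold or rule for choosing between the two.

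The null hypothesis in SAP 5 is that the "mean change from baseline in SIB total score between the two groups is the same", and SAP 7.5 says "inference will be based on type I error rate of 0.05". Protocol 9.4 names no test for the primary endpoint; protocol 3.1 names a two-sample t-test.

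**The concern.** A nominal 5% error rate belongs to one analysis fixed before unblinding. Here the same data could lead to several primary p-values, all consistent with the SAP. Four optional covariates, counting one severity measure, already give 2^4 = 16 ANCOVAs before the fallback is considered. The protocol title calls the trial confirmatory, and no multiplicity adjustment is planned, so the error rate of the single primary test carries the conclusion.

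The missing stratum works in the other direction. Stratified randomisation balances the stratum between arms. If the stratum predicts SIB change beyond baseline SIB, a model without it overstates the standard error: the test becomes conservative and some power is lost.

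The fallback also changes what is estimated. A rank-ANCOVA effect is in ranks, whereas the hypothesis is stated in mean SIB change.

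**Working it through.** **1. The plan's own power.** Inputs from SAP 3: SDs of change 6.8 (20 µg) and 6.7 (placebo), 50 or 37 per arm, two-sided alpha 0.05, two-sample t-test. The noncentrality is d / (SD × √(2/n)). For d = 4.0, n = 50, SD 6.8 this is 4.0 / (6.8 × 0.2) = 2.94 on 98 df.

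- 50 per arm, 4.0 / 4.5 / 5.0 / 5.5 points: 83.0, 90.6, 95.4, 98.0% (stated 83, 91, 95, 98).
- 37 per arm, 4.5 / 5.0 / 5.5 points: 80.2, 87.7, 93.0% (stated 80, 88, 93).

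The stated power reproduces and is not in dispute.

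**2. Leaving out the stratum.** The documents do not say how strongly the stratum predicts change once baseline SIB is known, so its partial R² is assumed to be 0, 2, 5 or 10%. With exact balance, size ≈ 2Φ(−1.96/√(1−R²)). At R² = 0.10 that is 2Φ(−2.066) = 3.9%, and the confidence interval is 1/√0.90 = 1.054 times as wide as it should be.

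Simulation: 20,000 trials per cell, 100 randomised, strata 50:50, blocks of 4 within stratum (assumed), residual SD 6.8, correlation of stratum with baseline SIB 0 or 0.6. The 37-per-arm case keeps a random 74 subjects. Size and interval width are for 50 per arm; power changes are in percentage points from adding the stratum.

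| Assumed partial R² | Size without stratum | Excess CI width | Power change, 4.0 points, 50 per arm | Power change, 4.5 points, 37 per arm |
|---|---|---|---|---|
| 0% | 4.9-5.0% | 0% | -0.2 to 0 | -0.4 to -0.3 |
| 2% | 4.9-5.0% | 1% | +0.4 to +0.6 | +0.1 to +0.5 |
| 5% | 4.4-4.7% | 2.5% | +1.2 to +1.6 | +1.3 to +1.6 |
| 10% | 4.2-4.3% | 5.5% | +2.4 to +3.0 | +3.0 to +3.1 |

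A separate simulation at 37 per arm, with assumed stratum effects of 0, 3 and 6 points, agrees. Size without the stratum is 5.1, 4.6 and 4.0%; with it, 4.8, 4.8 and 4.9%. Power at 4.5 points moves from 80.6 to 80.3%, 81.7 to 82.7% and 84.1 to 87.8%.

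**3. Open covariate choice, worst case.** 4,000 null trials per setting, 50 per arm, smallest p over the 16 covariate sets. The imputation version has 25% missing at Week 13 and 10% at Week 9 (monotone, at random), predictive mean matching, 20 imputations and Rubin's rules. Monte Carlo SE is about 0.4 percentage points.

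| Assumed share of residual variance per covariate | Type I error, multiple imputation | Type I error, complete data | Complete data, range including repeat runs |
|---|---|---|---|
| 0% | 5.5% | 5.7% | 5.7-6.9% |
| 2% | 7.4% | 8.7% | 7.7-8.7% |
| 5% | 8.2% | 9.8% | 9.0-10.0% |

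Models fixed in advance stayed at 4.2 to 5.7%. With a different option set (eight covariate sets, rank-ANCOVA and Mann-Whitney; severity not varied, 37 per arm), the smallest p gave 6.7 to 7.3%.

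**4. Fallback.** 5,000 null trials at 37 and 50 per arm, complete data, normal, t(3) and skewed gamma errors. The SAP names no gate, so Shapiro-Wilk p < 0.05 on residuals was assumed.

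- One fallback named in advance: 4.6 to 5.3%. The switch itself does not inflate.
- Smaller of the rank-ANCOVA and Wilcoxon p-values: 5.0% with normal errors, 5.6 to 6.7% with heavy-tailed or skewed errors.

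**The case against.** SAP 8.2.1 does name a specific and valid model. Omitting the stratum creates no false-positive risk, baseline SIB is itself a measure of cognitive severity, and the gain is material only if the stratum carries substantial further information, which no document shows. That stands: taken alone, the stratum is a minor efficiency point.

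The error rates in step 3 are ceilings. They require that the most favourable of 16 p-values be reported, with prognostic strengths the documents do not give; with no prognostic value the imputation figure is 5.5%. The fallback and 37-per-arm results use complete data, whereas the planned analysis is FAS with multiple imputation. These limits stand and are stated with the numbers.

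SAP 7.6 could be read as permitting supportive adjusted analyses only. That does not hold: it names the primary endpoint explicitly.

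One named fallback with an objective trigger would also close that gap; moving the rank analysis to sensitivity is a preference, based on SAP 5 being stated in mean change.

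On the protocol's t-test, protocol 9 gives the SAP precedence, so the t-test does not compete as the primary test. The same section also requires a modified primary analysis to be reflected in a protocol amendment, so the mismatch with protocol 3.1 still needs correcting.

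**Conclusion.** The concern holds and should be fixed before unblinding. The stratum is missing from the named model, covariate use is open-ended, and the fallback has neither a trigger nor a single method. Nothing else in either document settles these points.

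The stated power is sound. Omitting the stratum makes the test accurate to mildly conservative. In the main range (assumed partial R² 0 to 10%), adding it changes power by about -0.4 to +3.1 points.

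The weightier part is the unfixed choice. Under the assumed covariate strengths, worst-case type I error is 5.5 to 8.2% with imputation and up to about 10% with complete data, against the 5% on which SAP 7.5 relies. The SAP does not say such selection will happen; it does not prevent it.

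**What to change.** - **SAP 8.2.1:** state the primary test as ANCOVA of Week 13 change in SIB total score with fixed terms for treatment, baseline SIB and MMSE-2 stratum as randomised. Keep one named rank-ANCOVA with the same terms as a sensitivity analysis, not a replacement.
- **SAP 7.6:** replace the permissive list with these terms. Allow age, sex and a defined severity measure only in labelled sensitivity analyses.
- **SAP 8.2.2.1:** use the same model at Weeks 5, 9 and 15.
- **SAP 8.2.2.2 and 8.2.2.3:** specify treatment and baseline SIB only, because a stratum term cannot be estimated within one stratum.
- **Protocol 3.1 and 9.4:** align both with this ANCOVA at the next amendment.

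The cost is one degree of freedom (at most about 0.4 power points if the stratum is uninformative), SAP wording, and a protocol amendment with IRB approval (protocol 11.0 and 12.6). No new data are needed.
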